Descriptive analysis of the participant demographics and the image acquisition parameters will be undertaken, including patient preference and thematic analysis of any free text comments from the radiographer or patient. Comparison of examination length will be undertaken utilising the 'start time' and the time on the last image in that orientation, it is acknowledged this outcome will be influenced by the need for repeat exposures and technical difficulties in this small cohort.

Initial image quality will be assessed in relation to the diagnostic value of the radiograph and whether a repeat x-ray would have been warranted, this will allow comparison of repeat rates for the 2 examinations as well as the reasons. Further assessment of image quality will use a previously validated psychometric scale³¹ to compare the noise at different anatomical regions. This will provide a comparison between the 2 projections, the images will be randomly allocated for analysis and reviewers will be blinded to the acquisition technique (erect or supine) for this analysis to reduce bias and maintain objectivity.

Ethical Consideration

The key ethical issue associated with this research is the requirement for an additional x-ray in phase three. Other options have been explored including using only an anthropomorphic phantom and randomization of patients to either examination. These strategies do not provide sufficient robustness to demonstrate changes on an individual basis and the phantoms have fixed bony and soft tissue anatomy and therefore do not allow comparison of changes related to posture.

REC and HRA approval will be sought to ensure the additional radiation dose is managed within an appropriate framework. This will include establishing protocols to limit radiation exposure through exclusion from the study if repeat x-rays are required due to quality reasons. A patient will only have one radiograph taken in the erect position, regardless of final image appearances. This will ensure that the maximum additional dose for a single patient is limited to one exposure whilst maintaining the integrity of their clinical examination. This will also provide information regarding the potential repeat rate for erect radiographs in a prospective future trial. The study team will then decide whether the patient is excluded from the study, included for limited analysis or fully included despite imaging appearances, on a case by case basis.

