Appendix 7. Phase 3: Data collection sheet

A study to compare supine and erect pelvis radiographs – assessment of impact on radiation dose and diagnostic markers (SEPRAIDD)

Study ID Number:			Imaging order
Patient Hospital Number:			
Height:	m _	Weight:	kg
Age:		Gender:	M / F
Supine radiograph Start time:	Repe	at Yes/No	
kV	kV _		
mAs	mAs		
DAP	DAP		
EI Image time:	EI		
Erect radiograph Start time:	Сог	nments:	
kV			
mAs			
DAP			
EI Image time:			
Patient preference			
Supine / Erect			

Radiographer code:

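### Patients may be excluded on how their images turned out, with no set criteria, although image quality and repeats are compared outcomes; and examination time can include repeats for supine only

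*Protocol*

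**What the plan says.** Five statements in the protocol bear on this.

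- **Exclusion for repeats** (Ethical Consideration). Protocols are to be established to "limit radiation exposure through exclusion from the study if repeat x-rays are required due to quality reasons". The position is not named.
- **One erect exposure** (same section). "A patient will only have one radiograph taken in the erect position, regardless of final image appearances".
- **Decision after imaging** (same section). "The study team will then decide whether the patient is excluded from the study, included for limited analysis or fully included despite imaging appearances", case by case. No criteria are given. Blinding is stated for the image review under Phase Three, Data analysis, but not for this decision.
- **Outcomes** (Phase Three, Data analysis). Image quality is first judged on diagnostic value and on "whether a repeat x-ray would have been warranted, this will allow comparison of repeat rates for the 2 examinations as well as the reasons". Examination length runs from the start time to "the time on the last image in that orientation"; the protocol concedes that repeats and technical difficulties will affect it.
- **Recording** (Appendix 7). The block headed "Supine radiograph Start time" has a repeat yes/no field and a second set of kV, mAs, DAP and EI. The erect block has one set and no repeat field.

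**The concern.** A poor image is both a result to be counted and a ground for removing the patient who produced it. If removal depends on the result, the remaining patients no longer represent those imaged. The comparison of repeat rates and image quality then partly reflects who was kept. The same choice determines who contributes to dose and examination time. Key research questions 1, 2 and 4 concern dose, image quality and examination time, and the protocol wants the erect repeat rate to inform the future trial.

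The wording also conflicts with itself. Exclusion when a repeat is needed does not sit with the option to include a patient fully, with a comparison of repeat rates in the same patients, or with a data sheet that provides for a supine repeat.

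A second, separate matter is that only supine can be repeated. Supine time can therefore contain a repeat and erect time cannot. The protocol's caveat on examination length does not mention this asymmetry. Nor does the text fix whether the first or the repeated supine image is set against the single erect image.

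**Working it through.** The protocol states no figure on this point, so there is none to reproduce. The sample size of 60 is the phase three minimum. Failure rates, the share of failures excluded and the minutes per repeat are not in the protocol and are assumed below.

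**Worst case for one position.** Suppose 6 of 60 erect films warrant a repeat.
- All counted: 6/60 = 10.0%, exact 95% CI 3.8% to 20.5%.
- All six excluded and uncounted: 0/54 = 0%, exact upper limit 1 − 0.025^(1/54) = 6.6%.

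**General form.** Let p be the true repeat-warranted rate in a position and f the share of those failures whose patients are excluded. With failures independent between positions, the observed rate is p(1 − f)/(1 − pf).

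Take true rates of 15% erect and 5% supine, a difference of +10 points:

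| Patients excluded | Erect | Supine | Difference (points) | Patients left of 60 |
|---|---|---|---|---|
| None | 15.0% | 5.0% | +10.0 | 60 |
| Half of erect failures | 0.075/0.925 = 8.1% | 5.0% | +3.1 | 60 × 0.925 = 55.5 |
| All erect failures | 0% | 5.0% | −5.0 | 60 × 0.85 = 51 |
| All supine failures | 15.0% | 0% | +15.0 | 60 × 0.95 = 57 |
| All failures in either | 0% | 0% | 0 | 60 × 0.85 × 0.95 ≈ 48 |

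With equal true rates of 10%, the observed difference is −10 points if all erect failures are excluded and +10 points if all supine failures are. Every row is compatible with the wording, so the direction cannot be predicted.

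**Examination time.** If patients with supine repeats are kept, the mean rise in supine time is the repeat rate times the minutes per repeat. At 5% and 2 minutes this is 0.05 × 2 = 0.1 minutes; at 10% and 5 minutes it is 0.10 × 5 = 0.5 minutes. Erect time has no counterpart.

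The two mechanisms are alternatives for any one patient. A patient excluded for a supine repeat cannot lengthen supine time, and one who is kept does not contribute to the selection.

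**The case against.** The best defence is that the protocol means to count failures. It says that the single erect exposure will inform the likely erect repeat rate, and the outcome is whether a repeat would have been warranted, which can be judged whether or not one was taken. Limited inclusion may mean counting the failure and leaving out only what cannot be measured. This is a single-arm pilot with largely descriptive analysis, and analysis sets are often left to a statistical analysis plan.

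Much of this stands. One-sided repeating does not by itself distort the repeat-warranted outcome, and 0 of 54 needs every failure to be both excluded and uncounted. But outright exclusion is one of the three options and nothing limits its use. The protocol fixes a discretionary, result-dependent rule, which is more than leaving detail to a later plan.

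A reader might infer more than the text supports:

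- **Dose is biased by supine repeats.** Dose is calculated for each exposure and the sheet keeps the repeat apart from the first. Distortion would arise only if exposures were summed or the repeat replaced the first, and neither is stated. Selection of patients is the only route to dose that the text opens.
- **The deciding team knows the position.** The text is silent; it neither states nor excludes blinding of this decision.
- **Patients with a failed supine film leave before the erect one, so loss depends on order.** Order is random, but no timing is given for the exclusion.
- **Examination time is badly distorted.** The effect is small and partly acknowledged, and time including repeats has some relevance to service delivery. Only the asymmetry is missing from the caveat.

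**Conclusion.** The point holds as a risk built into the stated rule. The repeat-rate and image-quality comparisons, and the choice of patients for dose and time, are open to selection bias of unknown size and direction. It cannot be said that they are biased, or that one technique is favoured: excluding erect failures favours erect, and excluding patients with supine repeats favours supine. The figures above illustrate the possible range under assumed rates and independent failures; they are not predictions. The examination-time asymmetry is real but minor, at 0.1 to 0.5 minutes on the assumed inputs. The conflict between the exclusion sentence, the full-inclusion option, the repeat-rate comparison and the supine repeat fields needs no assumption and must be reconciled.

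**What to change.** Leave the limit of one erect exposure as it is, and change the analysis wording.

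1. Reconcile the exclusion-for-repeats sentence with the inclusion options, the repeat-rate comparison and Appendix 7. Whatever is settled about further exposures, say separately which images already taken stay in the analysis.
2. Count every non-withdrawn patient with a study image in the repeat-warranted analysis, judged by blinded reviewers on the first image in each position. Withdrawn patients stay out, as the protocol already requires.
3. Keep every non-withdrawn patient imaged in both positions in the dose and time comparisons, based on the first image in each position. Show supine repeats, with their dose and time, separately.
4. Replace the case-by-case decision with omission only of an individual measurement that a blinded reviewer cannot make under criteria set in advance. Report the number and reasons by position.
5. Present any restricted set as a sensitivity analysis.
6. Add to the examination-time caveat that only supine can be repeated.

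The cost is wording in two sections, a first-image time for supine on the data sheet, and a step to ensure that first supine images are in the study file. No extra exposures or patients are needed.

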Appendix 3. Phase 1: Data collection instructions

A study to compare supine and erect pelvis radiographs – assessment of impact on radiation dose and diagnostic markers (SEPRAIDD)

Preparation

Patient will have been greeted by a GCP trained radiographer who will introduce themselves and explain the study, prior to obtaining consent. If consent is gained then the patient will complete paperwork and be asked to change in to a gown as required for their examination.

If the examining radiographer is different to the one obtaining consent repeat ID checks should be undertaken following introduction of self. Confirmation of participant agreement to proceed should be sought verbally.

Study procedure

Height and Weight should be undertaken on the study calibrated weigh scale, in cm and kg.

A disposable 150cm tape measure should be used to measure body circumference at the levels of the lower costal margin, the iliac crests and the greater trochanter. Source-patient distance will be measured using the built in tape measure on the x-ray tube within the room.

- 1. The patient should be positioned AP against the erect bucky. The tape is passed around their body, the appropriate landmark palpated ensuring that the tape is parallel to the floor. The measurement should be taken whilst the patient is in arrested expiration and recorded on the data collection sheet. This is repeated for all three anatomical levels.
- 2. The patient should be asked to remain in the same standing position whilst the tube head is positioned at 115cm SID. The light beam is used to centre the tube at the level of the iliac crests. Measurements are taken, using the built in tape measure at the tube head, in the midline at the level of the lower costal margin, iliac crests and greater trochanters (to correlate with tape measure circumference readings). Arrested expiration should again be utilised.
- 3. The patient is then asked to lie on the bucky table which is then set at its normal height. Tape measurements of body circumference are again made at the same three levels, this time ensuring that the tape measure remains perpendicular to the table top. The tube head is placed at 115cm SID, above the patient, and centred in the midline at the level of the lower costal margin. The built in tape measure at the tube head should be used to take a measurement at the level of the lower costal margin. The floating table top is then used to repeat these measurements centred over the iliac crests and greater trochanters.
- 4. The patient should then be thanked for their cooperation and their radiographic examination is undertaken.
- 5. The tape measure should be disposed of following completion of the examination.

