This study aims to ensure that X-ray images of the pelvis are performed using evidence based protocols. It will also determine if patient posture (erect or supine) has an effect on radiation dose, image quality and diagnostic measures.

[figure not shown]
The study objectives are to:

- Develop trial procedures, imaging protocols and patient information for a future study
- Estimate the recruitment rate for a prospective study which will the diagnostic and dose differences between supine and erect pelvic radiographs
- Identify the recruitment and refusal rates to such research.

Study site

A single NHS Trust is being used to control for variations in technique and equipment. Mid Yorkshire Hospitals NHS Trust (MYH) comprises 3 hospital sites, Dewsbury District Hospital, Pinderfields Hospital (Wakefield) and Pontefract Hospital. Almost 8000 adult patients were referred from either their GP or as an outpatient to the Trust radiology department for pelvis or hip radiographs in 2016, including those referred for a hip x-ray where a full pelvic radiograph is performed as standard. The age profile of these patients is demonstrated in Figure 1. This demonstrates that the median age of this patient population is 65, with 80% of all patients being over 50 years in age.

Method

Phase One: Patient modelling

The initial data collection will focus on ascertaining the patient population and how physical characteristics (body shape) differs between the erect and supine positions. This will be through standardised measures obtained in both positions.

Sample size

A cohort of 180 patients who are attending for radiography of the hip or pelvis from either an outpatient (OP) clinic or their general practitioner (GP) will be recruited. Specifically the study aims to achieve a minimum of 30 patients in each of the following categories:

Underweight/Normal (BMI<25)

Overweight (BMI 25-30)

Obese/Morbidly obese (BMI>30)

Inclusion criteria

All patients who attend for radiographs of the hip or pelvis from a MYH OP clinic or their GP will be eligible for inclusion to the study. It is estimated that there are approximately 60 eligible patients per week attending each hospital site within the study organisation.

Exclusion criteria

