Patients who are under the age of 18, pregnant, are unable to stand unaided, have undergone lower limb surgery within the previous six months or are unable to provide written informed consent will be excluded from the study. A further exclusion will be related to patients who are unable to stand unaided, as the ability to weight bear would be a key component in performance of an x-ray in the erect posture.

Withdrawal

Any participant can withdraw from the study at any point prior to final data analysis, expected to be 1 month from end of recruitment. Their data will be excluded from the study and records destroyed, however the radiographs will be retained as part of the clinical record.

Recruitment process

Recruitment will take place over a 6-week period to allow for workflow variation and patient refusal. Reasons for patient refusal will be collated to inform a future trial.

A study patient information leaflet (Appendix 1) will be sent with appointment letters for potential recruits from the general practitioner. These patients will be identified by the radiology appointments team at the time of booking an examination. This will also be made available within the orthopaedic clinic to patients attending for an appointment. The information sheet will explain what the study is undertaking and what the research is looking at and explain the risks and benefits of taking part. This will allow time for potential recruits to read the patient information leaflet and, if required, approach the study team prior to being asked for informed consent.

Poster information will also be displayed within the hospital outpatient areas for patients to read prior to attending the radiology department.

When the patient attends the radiology department for their radiographs a member of the radiology team will confirm their eligibility to participate in the study. A GCP trained member of staff who is a fully qualified radiographer who works permanently within the radiology department will then approach the patient, introduce themselves and explain the study and research and what will be required from them to take part within the study. Informed written consent (Appendix 2) will then be gathered from each recruit prior to any data collection.

Data collection

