The recruited participant will be asked to change into a gown appropriate to their radiological examination and then taken to a private room (x-ray room) to maintain dignity and privacy. They will then have various measures undertaken by the research team member (see instruction sheet appendix 3).

These will include:

- Height (m)
- Weight (kg)
- Body circumference
- Source-Object Distance (i.e. x-ray tube to patient skin, as a proxy for body diameter)

A small group of radiographers will be trained to undertake the specific study parameters to ensure consistent data collection (Appendix 4). They will then continue with the radiographic examination as requested by the referring clinician.

Data analysis

The data collected will allow modelling of the change in patient body shape between the two projections. Variations in shape between BMI subgroup, gender and age will be assessed. Mean and standard deviations will be calculated if the resultant data are approximately normally distributed and median (ISR) measures will be determined for non-parametric data.

[figure not shown]
Phase Two: Phantom Experiment

An anthropomorphic phantom of the abdomen and pelvis will be used to investigate the optimal image acquisition protocol based on the anatomical changes identified in phase one. No patients will be recruited for this part of the study.

The outcome of the phantom study will be specific kV and mAs settings or automatic exposure control (AEC) settings for the different techniques and comparison of the phantom dose data with national diagnostic reference levels.

Based on the variation in mean measures between the different position and body habitus in phase one a Kyoto phantom will be physically altered with the addition of appropriately positioned soft tissue density mimicking material. This will enable multiple exposures of the phantom to be made at different distances and exposure factors to ascertain whether automatic exposure devices can be reliably used in both of the patient positions or whether specific exposure charts should be calculated regarding a patient's body habitus.

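### The 150 cm tape prescribed for phase one may be too short for an occasional participant in the open-ended obese category, and no rule covers a reading beyond it.

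*Protocol*

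**What the plan says.** Appendix 3 (Phase 1: Data collection instructions, Study procedure) names one instrument for girth: "A disposable 150cm tape measure should be used to measure body circumference at the levels of the lower costal margin". The same sentence adds the iliac crests and the greater trochanter. Step 1 takes these readings with the patient standing, and step 3 repeats them with the patient lying on the table.

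The Phase One sample size section plans for "A cohort of 180 patients who are attending for radiography of the hip or pelvis" and adds: "Specifically the study aims to achieve a minimum of 30 patients in each of the following categories". The top category is "Obese/Morbidly obese (BMI>30", which has no ceiling. The Phase One exclusions ("Patients who are under the age of 18, pregnant, are unable to stand unaided, have undergone lower limb surgery within the previous six months", and those unable to consent) contain no limit on weight, BMI or girth.

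Two other statements bear on the consequence. The Phase Two section uses the results by body habitus: "Based on the variation in mean measures between the different position and body habitus in phase one a Kyoto phantom will be physically altered". Appendix 3 also takes a second body-size measure with a different instrument: "Source-patient distance will be measured using the built in tape measure on the x-ray tube within the room". The Phase One data collection section lists that measure as "Source-Object Distance (i.e. x-ray tube to patient skin, as a proxy for body diameter".

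Neither the instructions nor the Appendix 4 data sheet mentions a longer tape, joining two tapes, or an entry for a girth beyond 150 cm.

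**The concern.** The instrument has a hard upper limit, but the population it is meant for has none. If a participant's girth at some level exceeds 150 cm, the radiographer must leave a blank, write 150 or improvise. Whether a reading is lost or capped then depends on its own size, so the loss is not random and it falls in the upper tail of the obese group. A participant might also exceed the limit in one posture only, which would remove or distort that participant's paired difference at that level.

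At stake is the mean circumference of the obese group and its erect-supine change. Both are among the phase one measures from which the phantom is adapted, and the phantom work in turn informs the exposure settings for phase three.

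**Working it through.** **Inputs from the protocol.** Tape limit 150 cm (Appendix 3). Phase one total 180, with at least 30 in each of three BMI categories (Phase One, Sample size). The protocol gives no mean, SD or expected proportion for girth, so there is no figure of its own to reproduce.

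**Size of the limit.** For a circular trunk, 150/π = 47.7 cm in diameter.

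**Obese group size.** 30 is the stated minimum. 60 would be an equal third of 180. 120 is the most possible if the other two categories hold only their minimum (180 − 2 × 30).

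**Assumption (not in the documents).** Girth at the widest level in the BMI>30 group is normal with mean μ and SD σ. Two sets of values were tried: μ 110 to 125 cm with σ 10 to 15 cm, and μ 118 to 128 cm with σ 12 to 15 cm.

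**Formulas.** With z = (150 − μ)/σ, φ and Φ the standard normal density and distribution function:
- proportion over the limit: p = 1 − Φ(z)
- expected number over: n × p
- chance of at least one over: 1 − (1 − p)^n
- fall in the group mean if readings are capped at 150: σ[φ(z) − z·p]
- fall in the group mean if readings are dropped: σφ(z)/Φ(z)

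| μ, σ (cm) | z | p | Expected of 30 | Expected of 60 | Fall if capped (cm) | Fall if dropped (cm) |
|---|---|---|---|---|---|---|
| 110, 10 | 4.00 | 0.003% | 0.0 | 0.0 | <0.001 | 0.001 |
| 118, 12 | 2.67 | 0.4% | 0.1 | 0.2 | 0.01 | 0.1 |
| 120, 12 | 2.50 | 0.6% | 0.2 | 0.4 | 0.02 | 0.2 |
| 122, 14 | 2.00 | 2.3% | 0.7 | 1.4 | 0.12 | 0.8 |
| 125, 15 | 1.67 | 4.8% | 1.4 | 2.9 | 0.30 | 1.6 |
| 128, 15 | 1.47 | 7.1% | 2.1 | 4.3 | 0.47 | 2.2 |

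In the middle case (120, 12) the chance that at least one participant exceeds the tape is 17% with 30 obese participants, 31% with 60 and 53% with 120. In the most extreme row, dropping the readings lowers the mean by 2.2 cm of girth, or 2.2/π = 0.7 cm of equivalent diameter.

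**Effect on the paired change.** Let a and b be a participant's true erect and supine girths. If both entries are capped at 150, then |min(a,150) − min(b,150)| ≤ |a − b|. Capping can therefore only shrink that participant's difference or leave it unchanged, and the recorded change is zero when both exceed 150. This needs no distribution. If the pair is missing instead, the effect on the group's mean change depends on whether change varies with size, which phase one has yet to find out.

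**The case against.** The strongest reply is that the problem may never arise. The protocol gives no girth data, and neither a BMI above 30 nor morbid obesity implies a girth above 150 cm. Excluding people who cannot stand unaided may thin the extreme tail further, though the documents do not allow this to be quantified. All of this stands, and it is why the point is put as a possibility.

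The second reply is that body size is also measured in another way. Source-patient distance is taken at the same three levels in both positions with the tube's own tape, so a participant beyond 150 cm still contributes a paired measure. The dose calculation uses source-object distance, mAs and kV, not circumference, and the phase three data sheet does not collect circumference. This also stands, and it confines the risk to circumference at the affected level. It does not remove the point: the distance is a midline proxy for diameter and does not capture sideways spread. Appendix 3 also takes it in order to correlate it with the tape readings.

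Third, the Phase One analysis allows medians when data are not normal, and a median is unmoved by capping a few high readings. That is true of capping, but blanks would still shift it slightly.

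A reader might infer three stronger things. One is that the largest participants certainly cannot be measured, which the documents do not show. Another is that the erect-supine change in the obese group is biased downwards, but the direction for the group is unknown. The third is that data are lost where posture change matters most. The Background says that obesity alters posture and that overlying abdominal tissue may affect dose. It does not say that the change between positions is greatest in the largest patients.

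**Conclusion.** The point holds as a minor measurement gap. A 150 cm tape is fixed for a group with no upper size limit, and nothing tells staff how to record a girth beyond it. About 0 to 2 of 30 obese participants might be affected (0 to 4 of 60), with a fall in the group's mean circumference of at most about 0.5 cm if readings are capped and 2.2 cm if they are dropped. These figures rest wholly on assumed normal distributions, and the upper ends come from the most extreme values tried. Without any such assumption, loss or capping of readings above 150 cm can only lower the recorded upper tail, and capping can never enlarge an individual's difference. The expected effect on the phantom inputs is small, and no figure stated in the protocol changes.

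**What to change.** In Appendix 3, replace the 150 cm tape with a longer disposable one, for example 200 cm. Add one line to the instructions and the Appendix 4 sheet: a reading still beyond the tape is recorded as over limit, not as the limit value, so that the analysis can recognise it as censored. The sample size and the measurement steps stay as they are. The only downside is a negligible consumable cost.

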Appendix 4: Phase 1: Data collection sheet

A study to compare supine and erect pelvis radiographs – assessment of impact on radiation dose and diagnostic markers (SEPRAIDD)

Study ID Number:				
Patient Hospital Number:				
Height:	m	Weight:	kg	
Age:		Gender:	M / F	
Erect Position (Source-Centring):		(Lower cos	stal margin)	
		(Iliac crest	s)	
		(Greater ti	ochanter)	
Body circumference (Erect):		(Lower cos	stal margin)	
		(Iliac crest	s)	
		(Greater ti	ochanter)	
Supine Position (Source-Centring):		(Lower cos	stal margin)	
		(Iliac crest	s)	
		(Greater ti	ochanter)	
Body circumference (Supine):		(Lower cos	stal margin)	
		(Iliac crest	s)	
		(Greater ti	ochanter)	

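### Phase one source-patient distance is centred once when erect but at every level when supine, so the erect trochanter reading is too long and the erect-supine change in thickness is biased

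*Protocol*

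**What the plan says.** Under Phase One, Data collection, the protocol lists "Source-Object Distance (i.e. x-ray tube to patient skin, as a proxy for body diameter" among the measures. Its Data analysis paragraph states the purpose: "The data collected will allow modelling of the change in patient body shape between the two projections". The Phase Two section then builds up a phantom from the average differences between postures and body types found in phase one.

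The measuring procedure is in Appendix 3.

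- **Step 2, erect.** The patient stays standing "whilst the tube head is positioned at 115cm SID". Then "The light beam is used to centre the tube at the level of the iliac crests". The readings follow: "Measurements are taken, using the built in tape measure at the tube head, in the midline at the level of the lower costal margin", and likewise at the crests and the trochanters. No movement of the tube between readings is mentioned.
- **Step 3, supine.** "The tube head is placed at 115cm SID, above the patient, and centred in the midline at the level of the lower costal margin". After that first reading, "The floating table top is then used to repeat these measurements centred over the iliac crests and greater trochanters".

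The Appendix 4 data sheet heads the three erect distance fields "Erect Position (Source-Centring" and labels the supine fields in the same way.

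**The concern.** The two postures are measured by different geometry. Supine, each level is brought onto the central ray before it is read, so every distance is perpendicular to the support. Erect, only the crest reading lies on the central ray. The other two are taken from a tube head set at crest height, so they run along the hypotenuse of a right-angled triangle.

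A slant distance always exceeds the perpendicular one, so the error has one sign. Erect distance is overstated, erect thickness is understated by the same amount, and the erect-minus-supine change in thickness is shifted downwards. Recruiting more patients does not remove a one-sided error. Unless the offset from the crests is recorded for each patient, later analysis cannot remove it either. At stake is the phase one change in thickness at the affected levels, and through it the amount of material added to the phantom in phase two.

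**Working it through.** The protocol states no figure on this point, so there is nothing to reproduce. The check is geometric.

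**Inputs from the protocol.** Source-to-image distance is 115 cm in both postures (Appendix 3, steps 2 and 3). There is one centring point erect and three supine (same steps). Phase one plans 180 patients, with at least 30 in each BMI category (Phase One, Sample size).

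**Assumptions, not in the protocol.** Front-to-back thickness 20-35 cm; distance from support surface to detector 0-5 cm; distance along the body from the crests (h) 3-10 cm to the lower costal margin and 12-20 cm to the trochanters; standard deviation of a patient's erect-supine change 1-3 cm.

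**Perpendicular distance.** s = 115 − gap − thickness. The extremes are 115 − 0 − 20 = 95 cm and 115 − 5 − 35 = 75 cm.

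**Error in an erect reading.** error = √(s² + h²) − s, in cm:

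| s (cm) | h = 3 | h = 10 | h = 12 | h = 15 | h = 20 |
|---|---|---|---|---|---|
| 75 | 0.06 | 0.66 | 0.95 | 1.49 | 2.62 |
| 80 | 0.06 | 0.62 | 0.89 | 1.39 | 2.46 |
| 85 | 0.05 | 0.59 | 0.84 | 1.31 | 2.32 |
| 90 | 0.05 | 0.55 | 0.80 | 1.24 | 2.20 |
| 95 | 0.05 | 0.52 | 0.75 | 1.18 | 2.08 |

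Worked example: with s = 90 and h = 15, √(8100 + 225) = 91.24, an error of 1.24 cm.

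**By level.**
- Iliac crests: h = 0, error 0.
- Lower costal margin (h 3-10): 0.05 to 0.66 cm.
- Greater trochanters (h 12-20): 0.75 to 2.62 cm.

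**Against random error.** The 95% half-width of a mean paired change is 1.96 × SD/√n.
- n = 180: 1.96 × 1/√180 = 0.15 cm to 1.96 × 3/√180 = 0.44 cm.
- n = 30: 1.96 × 1/√30 = 0.36 cm to 1.96 × 3/√30 = 1.07 cm.

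The smallest trochanter error (0.75 cm) exceeds the largest half-width at n = 180 (0.44 cm). At n = 30 it may or may not exceed the half-width, depending on the standard deviation and the offset. At the costal margin the error overlaps the random error at both sample sizes.

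**Dependence on body size.** At h = 15 the error is 1.49 cm when s = 75 and 1.18 cm when s = 95, a difference of 0.31 cm. The error is therefore not quite constant across body types.

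**After the change.** Centring at each level makes h = 0, so the error is 0 at all three levels.

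**The case against.** The strongest reply is that a stationary tube is inferred. Step 2 does not say that the tube stays where it is, the Appendix 4 label can be read as source to centring point at each level, and the measuring staff are few and trained. This limits how sure one can be that slanted readings would be taken in practice. It does not supply the missing instruction: step 2 names one centring point, while step 3 spells out re-centring. If some radiographers re-centre and others do not, the error becomes operator-dependent, which is no better.

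A second reply is that circumference is taken at the same three levels in both postures. That is true, and those readings are unaffected, so phase one retains a sound measure of shape. Circumference does not give front-to-back diameter, however, which is what the distance is meant to represent.

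A reader might infer more than the documents support:

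- **That two levels are equally biased.** They are not. At the costal margin the error is mostly a few millimetres.
- **That the erect exposure factors or doses in phase three will be wrong.** This is not shown. Phase two draws on mean measures generally and tries several distances and exposure factors, and the phase three data sheet records the actual exposure values.
- **That the error works against the expected effect of posture.** The Background speaks of abdominal tissue, but the sizeable error is at the trochanters.
- **That a difference in detector gap between erect bucky and table adds a further bias.** The protocol gives neither gap. A gap is a property of the room that can be measured at any time, and allowing for it is an analysis detail.

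**Conclusion.** The point holds in limited form. As written, Appendix 3 measures distance differently in the two postures, and the erect readings off the crest level are too long. The direction is certain if step 2 is followed literally. The size rests on assumed anatomy: about 0.75-2.6 cm at the greater trochanters, about 0.05-0.7 cm at the lower costal margin, and nil at the crests. At the trochanters this is larger than the sampling error of the mean change in 180 patients across the assumed range. The consequence that can be supported is a biased phase one change in distance that can carry into the phantom build-up, and no further.

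**What to change.** Reword Appendix 3 step 2 so that the tube is moved vertically and centred with the light beam at each of the three levels before that level is read, matching step 3. If the tube cannot be moved in a given room, add a field to the Appendix 4 sheet for the vertical offset from the crests and use √(reading² − offset²). For the worked example, √(91.24² − 15²) returns 90.0 cm.

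The cost is a change of wording and about a minute per patient. Recording a reference distance once per room is an optional help to the analysis and is not needed to resolve this point.
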